3.2.3 Secondary Endpoint Analysis

Whether there is a significant benefit of the BiCROS fitting over the unaided condition in terms of SRTs will be tested using a one-tailed paired samples t-test. The assumption of normally distributed paired differences between unaided and BiCROS will be tested by visually inspecting Q-Q plots, checking skewness and kurtosis against predefined thresholds (skewness < 0.8 and kurtosis < 2) and testing for statistically significant deviations from normality ($p < .05$) using the Shapiro-Wilk-test. Outliers will be defined as differences that lie outside the range between 1.5 times the interquartile range below the first quartile and 1.5 time the interquartile range above the third quartile of the data. Outliers will be removed if they are ≥ 2 standard deviations from the mean. In case of a non-normal distribution, non-parametric testing will take place with a one-sided Wilcoxon rank sum test.

Descriptive analysis with mean and standard deviations will be completed for the questionnaire results. In addition, repeated measures ANOVA with follow-up post hoc t-tests with Bonferroni correction as required will be performed comparing the responses of multiple sub-scales to 0 ("unchanged" - the questionnaire asks participants to rate their experience in terms of change (improvement vs. no improvement for each question) including an option for no change). Factors are conditions (unaided and BiCROS) and SSQ subscales (speech hearing, spatial hearing, and qualities of hearing). Violations of sphericity will be corrected by adjusting the degrees of freedom of the ANOVA using the Greenhouse-Geiser epsilon.

Sound quality ratings and listening effort ratings will be analyzed using repeated measures ANOVA with follow-up post hoc t-tests with Bonferroni correction as required. Factors are conditions (unaided, monaural with omnidirectional and beamformer, and BiCROS with omnidirectional and beamformer) and subscales (clarity, total Impression, and listening effort).

Preference ratings will be analyzed using one-sample Shapiro-Wilk test for normality to detect any significant skew toward a preferred setting, using BiCROS beamformer as the test condition for all comparisons.

According to common standards and Type I error probability of 5% is deemed to be acceptable and the null hypothesis will be rejected if the p -value is equal to or less than 0.05.

Time point of analysis: After all data collection of the primary endpoint is completed for all participants.

Responsibility for analysis: Western University investigators will complete the statistics.

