1.2 Primary and Secondary Objectives

The **primary objective** of this study is to evaluate whether a BiCROS fitting improves Speech Intelligibility for speech from the front and noise from the better ear's side compared to no treatment (unaided) for adults with unaidable hearing loss in one ear and aidable hearing loss in the other ear measured with the US Matrix Test.

The **secondary objectives** of this study are:

1. Evaluate whether a BiCROS fitting improves Speech Intelligibility in a setup with speech from the front and noise from the better ear's side compared to the alternative treatment of a monaural hearing aid fitting for adults with unaidable hearing loss in one ear and aidable hearing loss in the other ear measured with the US Matrix Test.
2. Evaluate whether a BiCROS fitting improves Speech Recognition Thresholds (SRT) by 1dB for speech from front in diffuse noise compared to no treatment (unaided) for adults with unaidable hearing loss in one ear and aidable hearing loss in the other ear measured with the US Matrix Test.
3. Evaluate whether a BiCROS fitting improves Speech Intelligibility in diffuse noise compared to the alternative treatment of a monaural hearing aid fitting for adults with unaidable hearing loss in one ear and aidable hearing loss in the other ear measured with the US Matrix Test.
4. Evaluate whether a BiCROS fitting results in improved subjective quality of hearing compared to no treatment (unaided) for adults with unaidable hearing loss in one ear and aidable hearing loss in the other ear measured with a questionnaire (SSQ).
5. Evaluate decrease in subjective listening effort for adults with unaidable hearing loss in one ear and aidable hearing loss in the other ear with a BiCROS fitting compared to no treatment (unaided) with a questionnaire or other means.

2 Design of the clinical investigation

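### The secondary SRT analysis repeats the primary test, so the two BiCROS-versus-monaural objectives have no test and the 1 dB objective is never tested against 1 dB

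*Combined protocol and SAP*

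**What the plan says.** Section 1.2 sets three secondary objectives on the US Matrix Test.

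- Objective 1: whether BiCROS "improves Speech Intelligibility in a setup with speech from the front and noise from the better ear's side compared to the alternative treatment", the alternative being a monaural hearing aid.
- Objective 2: whether BiCROS "improves Speech Recognition Thresholds (SRT) by 1dB for speech from front in diffuse noise compared to no treatment (unaided", that is, with a stated figure of 1 dB.
- Objective 3: whether BiCROS "improves Speech Intelligibility in diffuse noise compared to the alternative treatment of a monaural hearing aid fitting".

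Section 3.2.3 contains one SRT analysis for all of these. Its question is "Whether there is a significant benefit of the BiCROS fitting over the unaided condition in terms of SRTs", and its method is a paired t-test, one-tailed. The next sentence confirms which difference is meant: "The assumption of normally distributed paired differences between unaided and BiCROS will be tested". The whole paragraph is the same as the primary analysis paragraph in section 3.2.2.

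Monaural conditions are named as an analysis factor once, for other outcomes: "Sound quality ratings and listening effort ratings will be analyzed using repeated measures ANOVA", with the specification "Factors are conditions (unaided, monaural with omnidirectional and beamformer, and BiCROS with omnidirectional and beamformer) and subscales (clarity, total Impression, and listening effort". Section 3.2.1 lists Matrix SNRs from the hearing aid conditions as data but attaches no test to them.

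**The concern.** The secondary SRT paragraph appears to have been carried over from the primary without being adapted. Two things follow.

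First, BiCROS versus unaided mixes two effects: amplifying the better ear, and adding the transmitter on the poorer ear. Only BiCROS versus monaural separates them, and that is the contrast with no planned test. Section 2.1.1 lists two BiCROS and two monaural fittings that differ in microphone mode. Without a planned contrast, the pair reported could be chosen after the data are seen. That is a real weakness in a study that section 2.1.1 calls confirmatory and that section 1.1 says is meant to support claims.

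Second, an ordinary paired t-test that rejects at p ≤ 0.05 shows only that the mean gain exceeds zero. The 1 dB in objective 2 appears nowhere in the analysis, so objective 2 could be reported as met on a gain clearly smaller than 1 dB.

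**Working it through.** **Matching objectives to tests**

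| Secondary objective (1.2) | Comparator | Noise setup | Matching Matrix test in 3.2.3 |
|---|---|---|---|
| 1 | Monaural aid | Better-ear side | None |
| 2 | Unaided, 1 dB | Diffuse | Unaided contrast; noise setup not named; no 1 dB criterion |
| 3 | Monaural aid | Diffuse | None |

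This table establishes the main defect and needs no arithmetic.

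**The plan's own figures.** Section 3.1 gives 19 participants for 95% power and 12 for 80%, using a one-tailed paired t-test for the primary objective. It states no effect size or SD, so these cannot be reproduced from the document's inputs. They can be checked against each other. With exact noncentral-t power at one-sided 5%, N = 19 at 95% needs a standardised paired effect of 0.785 to 0.809, and N = 12 at 80% needs 0.766 to 0.806. The figures agree for effects of about 0.785 to 0.806; 0.80 gives exactly 19 and 12. If 1 dB had been the planning effect (an assumption), the SD would be about 1/0.80 = 1.25 dB. That is why 1.25 is included below.

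**Inputs for objective 2.** n = 19 (section 3.1); one-sided level 5% (section 3.2.3); SD of the paired SRT difference not given, so 1 to 3 dB is assumed. Gain = SRT unaided minus SRT BiCROS.

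**Formulas**

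- Smallest significant mean gain against a null of 0: t(0.95, 18) × SD/√19 = 1.734/4.359 × SD = 0.398 × SD.
- Probability of significance at true gain μ: P(T > 1.734), where T is noncentral t with 18 df and noncentrality μ√19/SD.
- For a null of 1 dB, replace μ by μ − 1.

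Example, SD 2 and μ = 1: noncentrality = 1 × 4.359/2 = 2.18, probability 0.67.

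| SD (dB) | Smallest significant mean, null 0 (dB) | Significant at true 0.5 dB, null 0 | Significant at true 1 dB, null 0 | Power at true 1.5 dB, null 1 | Power at true 2 dB, null 1 |
|---|---|---|---|---|---|
| 1 | 0.40 | 67% | 99.5% | 67% | 99.5% |
| 1.25 | 0.50 | 51% | 96% | 51% | 96% |
| 2 | 0.80 | 28% | 67% | 28% | 67% |
| 3 | 1.19 | 17% | 40% | 17% | 40% |

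The last two columns repeat the two before them because only μ minus the null matters. A test of more than 1 dB would reject 5% of the time at a true gain of exactly 1 dB; the planned test rejects 40% to 99.5%.

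The observed-mean threshold reaches 1 dB at SD = 1/0.398 ≈ 2.5 dB. Above that, a significant result needs an observed mean above 1 dB, but it still only rules out a true gain of zero. With all 23 participants the multiplier falls to 0.358, so smaller gains become significant.

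**The case against.** The strongest objection concerns the 1 dB limb. The objective does not call 1 dB a margin or a minimum; it could be the expected effect. The null of zero is also inferred, since section 3.2.3 speaks only of a significant benefit. On that reading the copied test, applied to the diffuse-noise data, properly supports some improvement over unaided, and the 5% benchmark does not apply. This is fair as far as it goes. But a paired t-test with no stated null is a test against zero, and the plan has no rule of any kind (shifted null, confidence limit or point estimate) that connects the result to 1 dB. The objective and the analysis still have to be reconciled.

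The probabilities rest on an assumed SD, and above about 2.5 dB the observed-mean argument no longer works. That stands; the figures are illustrative.

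On the monaural limb, objectives 1 and 3 speak of speech intelligibility rather than SRT. This does not rescue the plan: the primary objective uses the same term and is analysed as SRT. Matrix data from the monaural conditions fall within the planned dataset, but no analysis is assigned to them. Only secondary objectives are affected; the primary comparison stands apart from this point.

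**Conclusion.** The concern holds: the secondary SRT analysis is wrong as written. Objectives 1 and 3 have no planned test, which follows from the text alone and is the more serious half. Objective 2 has a test that cannot show a 1 dB gain. At n = 19, a treatment with half the stated gain would still reach significance between 17% (SD 3 dB) and 67% (SD 1 dB) of the time. Those figures assume normally distributed differences, an SD in that range and a null of zero. The conclusion that nothing in the analysis addresses 1 dB needs none of these. Three of the five secondary objectives therefore lack a matching analysis.

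**What to change.** In section 3.2.3, replace the copied SRT paragraph with one specification per objective.

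- **Objective 1:** one-tailed paired test of BiCROS versus monaural hearing aid SRT, noise from the better-ear side.
- **Objective 3:** the same contrast in diffuse noise.
- **Objective 2:** one-tailed paired test of H0: mean (SRT unaided − SRT BiCROS) ≤ 1 dB in diffuse noise, equivalently a one-sided 95% lower bound above 1 dB. Any non-parametric fallback needs the same shifted null. Alternatively, delete the 1 dB figure from objective 2 and claim only an improvement.

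Apply the normality and outlier checks to the difference used in each test. Name the microphone mode of each fitting compared; the BiCROS and monaural fittings listed in section 2.1.1 without the omnidirectional qualifier match the labels in the objectives. State how multiplicity is handled, since three separate one-sided 5% tests allow up to 3 × 5% = 15% for at least one false positive.

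The cost is wording: the conditions are already in the design. The price of the 1 dB test is power. At n = 19 and a true gain of 2 dB it is 96% at SD 1.25, 67% at SD 2 and 40% at SD 3; at a true gain of 1.5 dB it is 51% even at SD 1.25. Section 3.1 sizes the study for the primary objective only, so the sponsor should weigh these figures before choosing between the two options for objective 2.

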3.1 Determination of Sample Size

Primary objective

A power analysis was conducted to apply a one-tailed paired samples t-test to compare the difference between the two conditions tested in the primary objective. The required sample size for 95% power with a one-tailed paired t-test is 19.

With additional 4 participants as backup (based on previous research experience), the required number of participants is 23. For 80% power, 12 participants are needed.

Statistical criteria of termination of trial

There are no statistical criteria for stopping the study.

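### Optional improvement: Holm's step-down procedure in place of Bonferroni for the SSQ and rating post hoc t-tests would keep the same 5% family-wise error and never detect less

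*Combined protocol and SAP*

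**What the plan says.** Section 3.2.3 uses the same correction, "follow-up post hoc t-tests with Bonferroni correction as required", in two places. For the SSQ it plans "repeated measures ANOVA with follow-up post hoc t-tests with Bonferroni correction as required will be performed comparing the responses of multiple sub-scales to 0", where 0 means unchanged; the factors given are "Factors are conditions (unaided and BiCROS) and SSQ subscales (speech hearing, spatial hearing, and qualities of hearing"). For the other ratings, "Sound quality ratings and listening effort ratings will be analyzed using repeated measures ANOVA with follow-up post hoc t-tests with Bonferroni correction as required"; the factors are "conditions (unaided, monaural with omnidirectional and beamformer, and BiCROS with omnidirectional and beamformer) and subscales (clarity, total Impression, and listening effort"). The section closes with a 5% Type I error level.

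The text does not give the number of tests in each family, the sidedness of the post hoc t-tests, or what triggers the correction. The only power calculation, in section 3.1, concerns the primary contrast: "The required sample size for 95% power with a one-tailed paired t-test is 19" and "For 80% power, 12 participants are needed". It involves no Bonferroni correction.

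**The concern.** Unqualified, Bonferroni ordinarily means the single-step rule: each of m p-values is held to 0.05/m, however many of the others have already been rejected. Holm starts at the same threshold and relaxes it after each rejection, under the same family-wise guarantee. Where several true effects are present, the single-step rule therefore gives up some power.

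The tests concerned inform secondary objective 4 (subjective quality of hearing on the SSQ) and secondary objective 5 (listening effort). Recruitment is planned at 23, and section 3.3 says that dropouts will most likely not be replaced beyond that number. Lost power cannot easily be bought back with more participants.

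**Working it through.** **The plan's own figures.** The plan gives 19 participants (95% power) and 12 (80% power) for the primary one-tailed paired t-test, and 19 + 4 = 23. No effect size is stated, so they cannot be recomputed directly. Solving the noncentral-t power function backwards at one-sided 0.05, any standardised effect d from about 0.785 to 0.806 gives both 19 and 12, so the two are mutually consistent. There is no corresponding figure for the post hoc tests.

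**The two rules.** Order the p-values p(1) ≤ … ≤ p(m).
- Bonferroni rejects every p ≤ 0.05/m.
- Holm rejects p(i) while p(i) ≤ 0.05/(m − i + 1), and stops at the first failure.

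For m = 3, Bonferroni uses 0.05/3 = 0.0167 three times; Holm uses 0.0167, then 0.025, then 0.05. Three consequences need no simulation:
1. Holm's thresholds are never lower, so it rejects everything Bonferroni rejects.
2. Both compare the smallest p-value with 0.05/m, so the chance of at least one rejection is identical.
3. If m0 nulls are true, the first of them that Holm rejects stands at rank m − m0 + 1 or earlier, so its p-value is at most 0.05/m0. The family-wise error is then at most m0 × 0.05/m0 = 0.05, whatever the correlation.

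**Assumptions for the size of the gain (none is in the plan).** Two-sided paired t-tests; m = 3 for the SSQ (each subscale against 0); m = 10 for the ratings (all pairs of five conditions within one scale); effects in SDs of the paired difference; n = 19. The ANOVA step is not simulated.

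**SSQ, Bonferroni power at d = 0.6.** Noncentrality is 0.6 × √19 = 2.615. The two-sided critical value at 0.0167 on 18 df is 2.639. Power is 50.5%.

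**SSQ, power per true effect by simulation, n = 19.**

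| Subscales with a real effect | d = 0.5 | d = 0.6 | d = 0.79 |
|---|---|---|---|
| One | 34.5% vs 34.7% | about 50.4% vs 50.6% | not run |
| Two | not run | about 51% vs 54% | 78% vs 82% |
| Three | 35% vs 41–42% | about 51% vs 60% | 78% vs 86–88% |

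(Bonferroni first, Holm second. Correlation between subscales was 0 or 0.5 for d = 0.5 and 0.79, and 0.3 or 0.6 for d = 0.6; it changes the entries little.)

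The chance of rejecting all three at d = 0.6 is 19–20% vs 38% at correlation 0.3 and 27% vs 45% at 0.6. With n = 23 it is 31% vs 51% and 39% vs 58%.

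**Ratings, 10 pairs, n = 19.** Assumed means are 0, 0.8, 1.1, 1.3 and 1.6, in the order in which section 3.2.3 lists the conditions.
- A 0.8 SD difference: about 62% vs 70–71%.
- A 0.5 SD difference: about 20% vs 28%.
- BiCROS against unaided, 1.3 SD: 98.6% vs 99.2%.
- BiCROS against unaided, 1.6 SD: 100% vs 100%.

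**Realised family-wise error.**
- All nulls true: the same for both methods, between 4% and 5%.
- Three tests, two real at d = 0.79, n = 19: 1.7% vs 3.9–4.1%.
- Ten pairs, only unaided different: 2.6% vs 3.5%.

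**The case against.** The strongest reply is that this is a preference and not an error. Bonferroni is pre-specified and conservative. It cannot inflate false positives or bias an estimate, and it contradicts nothing else in the plan. That stands, and it is why the point is offered only as an improvement.

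Several stronger readings are tempting, and the documents do not support them.

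- *True findings are being discarded.* The plan states no effect size, SD, correlation, family size or power target for these tests. With one real SSQ effect the loss is 0.1 to 0.3 percentage points.
- *Objective 4 is badly underpowered because power for all three subscales nearly doubles under Holm.* Objective 4 does not ask for all three subscales to be significant, and the chance of at least one rejection does not change.
- *Objective 5 suffers materially.* That objective compares BiCROS with unaided. Under the assumed means this contrast is 1.3 to 1.6 SD and gains almost nothing; the visible gains fall on monaural against unaided and on aided against aided. If the true contrast were nearer 0.8 SD, the gain would be larger, but the plan gives no basis for either figure.
- *Bonferroni gives nothing in return.* It has a lower realised error when some effects are real, and it yields simple simultaneous intervals that match the tests. Section 3.2.3 plans no such intervals and accepts 5%, so in this plan the return is small, though not nil.

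It is also fair to say that the less settled matter in these sentences is the undefined family and the undefined trigger for correction. Substituting Holm does not cure that unless the families are named at the same time.

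**Conclusion.** The point holds as a low-cost efficiency improvement to secondary analyses. At the 5% family-wise level the plan accepts, Holm is never less powerful than Bonferroni. With three SSQ tests, n = 19 and 0.6 SD effects, the gain per true effect is negligible with one real effect, about 4 points with two and about 9 points with three. These sizes rest on assumed effects, assumed families, two-sided tests and the single-step reading of Bonferroni, which is the natural reading but is not spelled out. An ANOVA step in front could lower both sets of figures; it could not reverse their order. The primary test in section 3.2.2 and the sample size in section 3.1 do not depend on this correction.

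**What to change.** In both sentences of section 3.2.3, replace *Bonferroni correction* with *Holm (step-down Bonferroni) correction*. State that it is applied within the three SSQ subscale tests as one family, and within the condition comparisons for each rating scale as separate families. List those comparisons, since all pairs of five conditions give 10 tests and comparisons with one reference give 4. Report Holm-adjusted p-values.

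The cost is a wording change with no new data and no change to the sample size. Simultaneous confidence intervals that match Holm are less simple; if intervals are wanted, Bonferroni intervals can be shown and labelled descriptive. Realised family-wise error will be somewhat higher than under Bonferroni when some effects are real, but still at or below 5%.

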2.1 General

2.1.1 Design Type

This clinical investigation is an interventional study, conducted at one investigation site, with a confirmatory design. The investigation employs a single group of participants that will be tested in all conditions (cross-over) and be blinded towards the intervention condition they are tested in as much as possible (unaided can't be blinded).

Test conditions:

- Experimental intervention: BiCROS fitting: A CROS microphone transmitter is worn on the poorer, unaidable ear and the hearing aid on the better hearing ear.
- Control intervention: Monaural hearing aid fitting: One hearing aid is worn on the better hearing ear.
- Control intervention: BiCROS fitting: A CROS microphone transmitter (with omnidirectional microphone mode) is worn on the poorer, unaidable ear and the hearing aid (with omnidirectional mode) on the better hearing ear.
- Control intervention: Monaural hearing aid fitting: One hearing aid (with omnidirectional mode) is worn on the better hearing ear.
- No intervention: No treatment (unaided), i.e. no CROS transmitter and no hearing aid are worn. (Condition not included in preference ratings because it doesn't allow for quick AB comparisons.)
- The order of conditions will be randomized.

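### Section 3.2.3 gives the SSQ change score a condition factor it cannot contain, and leaves the BiCROS-versus-unaided effort contrast undefined in mode, sidedness and family size

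*Combined protocol and SAP*

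**What the plan says.** Section 1.2 sets two patient-reported secondary objectives, each asking for one comparison. Objective 4: "Evaluate whether a BiCROS fitting results in improved subjective quality of hearing compared to no treatment (unaided"). Objective 5: "Evaluate decrease in subjective listening effort for adults with unaidable hearing loss in one ear", again BiCROS against unaided.

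For the SSQ, section 3.2.3 explains that participants rate change, with 0 meaning unchanged. It plans a repeated measures ANOVA with Bonferroni-corrected follow-up t-tests where needed, "comparing the responses of multiple sub-scales to 0". It then lists the factors: "Factors are conditions (unaided and BiCROS) and SSQ subscales (speech hearing, spatial hearing, and qualities of hearing").

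For sound quality and effort, the same section plans one repeated measures ANOVA over five conditions (unaided, and monaural and BiCROS each in two microphone modes) and three "subscales (clarity, total Impression, and listening effort"). Follow-up is again by Bonferroni t-tests where needed. The section does not say which contrasts are in the family, whether they are one- or two-sided, or which BiCROS mode answers objective 5.

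Two passages bear on the mode. Section 2.1.1 lists "Control intervention: BiCROS fitting: A CROS microphone transmitter (with omnidirectional microphone mode") among the controls, and the preference analysis in 3.2.3 proceeds "using BiCROS beamformer as the test condition for all comparisons".

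**The concern.** The SSQ description contradicts itself. A rating of change already contains the comparison with the reference state, so there is no separate unaided score to fill one level of a condition factor. The analyst must either invent that level or drop it, and the two choices give F tests of different questions. The text does not say whether the comparison with 0 goes ahead regardless of the F, nor whether an overall score or the separate subscales decide objective 4. Table 1 in section 2.2.1 mentions two questionnaires without naming them, so it does not settle the matter.

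For effort, the condition main effect averages effort with clarity and total impression, and the interaction asks whether the condition profile differs between scales. Neither is a test of BiCROS versus unaided on effort. That test exists only as a follow-up contrast, and its power depends on choices that could still be made after the data are seen. Section 2.1.1 calls the design confirmatory, so these choices should be fixed in advance.

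**Working it through.** **The plan's own figure.** Section 3.1 gives N=19 for 95% power (one-tailed paired t-test) and N=12 for 80%, to "compare the difference between the two conditions tested in the primary objective". It states no effect size, so N cannot be reproduced forwards. Solving backwards with the noncentral t at one-tailed 0.05, both figures fit a standardised paired difference (dz) of 0.785 to 0.806. At dz = 0.80, power is 95.6% at n=19 (94.6% at 18) and 82.9% at n=12 (79.5% at 11). This concerns the primary SRT comparison. Using 0.8 SD for SSQ or effort below is an assumption, with 0.5 SD as a less favourable case.

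**SSQ, unaided coded as 0.** Let mᵢ be participant i's mean change over the three subscales, with mean D and SD s.
- Condition sum of squares: 3 × n × 2 × (D/2)² = 3nD²/2, on 1 df.
- Error mean square: (3/2)s², on n−1 df.
- F = nD²/s² = t², the squared one-sample t of mean change against 0. On simulated data both came to 8.552.

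This reading validly tests objective 4, provided change is rated relative to unaided.

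**SSQ, factor dropped.** Only the subscale F remains. Assumptions: n=19, change SD 1, equal gain on all subscales, between-subscale correlation 0.5, two-sided, 20,000 simulated trials.

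| Gain | Mean change vs 0 | Subscale F | Any of 3 at 0.05/3 | All 3 |
|---|---|---|---|---|
| 0.8 SD | 98.0% | 5.1% | 95.0% | 58.8% |
| 0.5 SD | 71.6% | 5.0% | 60.2% | 12.2% |

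Analytic check at 0.8 SD: the SD of the three-subscale mean is √[(1 + 2×0.5)/3] = 0.816; dz = 0.8/0.816 = 0.980; noncentrality 0.980 × √19 = 4.271; critical t (18 df) 2.101; power 98.1%. The last two columns show that the unstated success rule (any subscale or all) also matters.

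**Effort, the contrasts.** Five conditions give 5×4/2 = 10 pairs within effort and 10×3 = 30 over the three scales. Two of the ten are BiCROS versus unaided, one per microphone mode. Plausible Bonferroni families are therefore m = 2 (both BiCROS modes vs unaided), 4 (each aided condition vs unaided), 10 or 30. The plan commits to none.

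**Effort, the power.** Two-sided noncentral t at level 0.05/m, noncentrality dz√n. At n=19 and dz=0.8 this is 0.8 × √19 = 3.487.

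| m | Level | Critical t (18 df) | n=19, 0.8 SD | n=19, 0.5 SD | n=23, 0.8 SD |
|---|---|---|---|---|---|
| 1 | 0.05 | 2.101 | 90.9% | 54.1% | 95.6% |
| 2 | 0.025 | 2.445 | 84.1% | 41.5% | 91.5% |
| 4 | 0.0125 | 2.775 | 75.3% | 30.7% | 85.6% |
| 10 | 0.005 | 3.197 | 61.7% | 19.5% | 75.3% |
| 30 | 0.00167 | 3.692 | 44.9% | 10.6% | 60.4% |

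Like for like with one-tailed tests (n=19, 0.8 SD), a single contrast has 95.6%, against 90.9 / 84.1 / 72.1 / 55.5% for m = 2 / 4 / 10 / 30. The step from 90.9% to 95.6% for a single contrast comes from the choice of side, not from removing the family.

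**Effort, the omnibus tests.** Simulated case (n=19): 0.8 SD gains in clarity and impression in all aided conditions, none in effort. The condition main effect was significant in 98.7% of trials (between-scale correlation 0) or 80.9% (0.5), while a direct BiCROS-versus-unaided effort test stayed at about 5%. A significant condition effect therefore says nothing specific about effort.

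**The case against.** The strongest reply is that the plan already reaches both objectives. The comparison of SSQ responses with 0 is written down; with the factors as listed and unaided set to 0, the condition F is the correct test; and Bonferroni follow-up includes BiCROS versus unaided on effort. All of this stands.

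A reader might infer that objectives 4 and 5 are left untested, or that the planned SSQ analysis has 5% power. The documents do not support either. The 5% belongs to the subscale F after the listed condition factor is dropped, and even then the comparison with 0 remains in the text. A reader might also infer that an omnibus F would be taken as proof of an effort benefit; section 3.2.3 never says so. The simulated case above shows only what the main effect fails to isolate. It is not matched to any effort-only case, so it cannot support a claim about how often the omnibus tests mislead relative to how often they succeed.

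It is also fair to say that the larger power losses come from families of 10 and 30, to which the plan does not commit, and that powering only the primary objective is not in itself a fault. With the directly relevant family of 2, the two-sided loss at 0.8 SD is 90.9 − 84.1 = 6.8 percentage points at n=19.

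What the reply does not remove is the contradiction in the SSQ model and the absence of a stated mode, side and family for effort.

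**Conclusion.** The concern holds as one of inconsistency and under-specification, not of missing tests. The SSQ factor list cannot be applied to a change score without inventing a level; one resolution gives the right test and the other leaves benefit to follow-up tests whose conditions are unclear. The effort comparison is reachable, but as two candidate contrasts in an undefined family. Under the assumed 0.8 SD at n=19, two-sided, that leaves power anywhere from 84.1% (family of 2) to 44.9% (family of 30), against 90.9% for one planned contrast; at 0.5 SD the range is 41.5% to 10.6%, against 54.1%.

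These figures are illustrative, because the plan gives no effect size for SSQ or effort; the direction of the loss does not depend on them. The SSQ conclusion assumes that change is rated relative to unaided, which the text implies but does not state. The change should be made before analysis; it concerns secondary objectives and does not touch the primary one.

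**What to change.** **SSQ (objective 4).** Delete the condition factor. Test mean SSQ change (equal-weight mean of the three subscale scores) against 0 with a one-sample t-test, or Wilcoxon signed-rank if non-normal, two-sided at 0.05 and not conditional on any F. This gives the same p-value as the zero-coded condition F, so nothing is lost against that reading. Report the three subscales against 0, Bonferroni-adjusted over 3, as supporting tests. State that change is rated relative to unaided. The equal-weight mean is a proposal; the plan names no overall score.

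**Listening effort (objective 5).** Take effort out of the subscale factor and analyse it as its own outcome, with one pre-specified paired test of BiCROS versus unaided. Use the beamformer mode, since section 2.1.1 labels omnidirectional BiCROS a control and section 3.2.3 takes BiCROS beamformer as the test condition for preference. This is an inference, because objective 5 names no mode, and the sponsor should confirm it. Make the test one-tailed at 0.05, matching the SRT tests and the direction stated in objective 5, with Wilcoxon signed-rank if non-normal. Keep the five-condition ANOVA with Bonferroni for clarity, total impression and exploratory effort contrasts, and list each comparison family.

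**Cost.** SAP wording only; no new data or visits. The planned effort contrast is no longer Bonferroni-adjusted against the other effort comparisons, and part of its power gain comes from that. Those other comparisons become exploratory, and single SSQ subscales become supporting. Objectives 4 and 5 are each tested at the full 0.05.
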